- 2) Days 3-6: All subjects will be seen on the CRSU on days 3 and 6, and at the IDAS clinic on days 4 and 5. On days 3-6, subject group A will receive one placebo pill twice daily, and group B will receive one placebo pill in the morning and one matching lorcaserin 10 mg pill in the evening, for a total dose of 10 mg daily. ECG with QTc will be performed daily. If the QTc is prolonged greater than 30ms over baseline lorcaserin dosage will be held.
- 3) Day 7: All subjects will receive one placebo pill in the morning in single blind fashion. Following Cocaine Self-administration sessions and impulsivity testing the subjects will leave the unit.
- 4) Days 8-10: All subjects will be seen at the IDAS clinic on Days 8 and 9 and subjects in group B will have a blinded dosage increase to 10 mg of lorcaserin twice daily for Days 8-11 (Days 10 and 11 will take place at the CRSU). Vital signs including heart rate, blood pressure and respiration rate will be obtained before placebo/lorcaserin administration. ECG with QTc will be performed daily under the supervision of a study physician. If the QTc is prolonged greater than 30ms over baseline lorcaserin dosage will be held.
- 5) Day 11: All subjects will be seen on the CRSU and receive placebo/lorcaserin in the morning followed by the last cocaine self-administration session.
- 6) Day 12: Subjects will be seen at IDAS for study procedures.
- 5) Cocaine Infusion Sessions (Days 1, 2, 6, and 10): All subjects will undergo an ascending dose intravenous cocaine administration after admission on day 1 to ensure safety of later cocaine studies.

To assess the safety and subjective effects of cocaine in the presence of lorcaserin, subjects will receive ascending doses of intravenous cocaine (10 mg, 20 mg, 40 mg), with each cocaine administration separated by

one hour. In addition, 0 mg cocaine (saline) infusion will be randomly given after the first dose of cocaine in order to aid in blinding investigators and subjects to the order of drug administration. Infusions will be carried out hourly starting from 1 hour after placebo/lorcaserin for 4 times (on Day 1, 2, 6, and 10). An example dose by session diagram is shown below. Note that the 0 mg dose is randomly given after the first dose of cocaine. Monitoring will be continued for 1 hour after the last dose of cocaine.

Dose	Dose Session 1	Dose Session 2	Dose Session 3	Dose Session 4
1	10 mg Cocaine	10 mg Cocaine	10 mg Cocaine	10 mg Cocaine

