Record brief substance craving scale and AE.
Administer COWS if opioid user.
Update concomitant medications.
Conduct clinical assessments (POMS, CGI-I, and C-SSRS).
Administer placebo/lorcaserin in evening
Leave IDAS.

Study Day 6

Arrive on CRS unit
Administer placebo in morning
Collect urine for pregnancy test and urine drug screen.
Perform and record Breathalyzer and vital signs.
Perform a 12-Lead ECG and continuous cardiovascular monitoring.
Record brief substance craving scale, VAS, and AE.
Administer COWS if opioid user.
Update concomitant medications.
Administer cocaine for PK.
Measure lorcaserin PK
Administer cocaine for Dosing session 3.
Conduct clinical assessments (POMS, CGI-I).
Administer placebo/lorcaserin in evening
Leave CRS unit.

Study Day 7

Arrive on CRS unit
Administer placebo in morning
Collect urine for pregnancy test and urine drug screen.
Perform and record Breathalyzer and vital signs.
Perform a 12-Lead ECG and brief physical exam.
Record brief substance craving scale, VAS and AE.
Administer COWS if opioid user.
Update concomitant medication.
Self -Administered cocaine session 3 in morning.
Self -Administered cocaine session 4 in afternoon.
Conduct clinical assessments (POMS, CGI-I).
Administer IMT task.
Leave CRS unit

Study Day 8

Arrive at IDAS

Administer placebo/lorcaserin in morning

Collect urine for pregnancy test and urine drug screen.

Perform and record Breathalyzer and vital signs.

Administer COWS if opioid user.

Perform a 12-Lead ECG and brief physical exam.

Record brief substance craving scale, VAS and AE.

Update concomitant medications.

Conduct clinical assessments (POMS, CGI-I, and C-SSRS).

Administer placebo/lorcaserin in evening.

Leave IDAS.

Study Day 9

Arrive at IDAS

Administer placebo/lorcaserin in morning

Collect urine for pregnancy test and urine drug screen.

Perform and record Breathalyzer and vital signs.

Perform a 12-Lead ECG.

Record brief substance craving scale and AE.

Administer COWS if opioid user.

Update concomitant medications.

Conduct clinical assessments (POMS, CGI-I, and C-SSRS).

Administer placebo/lorcaserin in evening.

Leave IDAS.

Study Day 10

Arrive on CRS unit

Administer placebo/lorcaserin in morning

Collect urine for pregnancy test and urine drug screen.

Perform and record Breathalyzer and vital signs.

Perform a 12-Lead ECG and continuous cardiovascular monitoring.

Record brief substance craving scale, VAS, and AE.

Administer COWS if opioid user.

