Procedure Afternoon Session	Cocaine Self Administration Depart from CRS			Three Doses of Cocaine (NexFin monitoring) Cardiovascular & Subjective Ratings Cardiac Biomarkers (4-6 hrs from last dose) Depart from CRS	Cocaine Self Administration Impulsivity Testing Depart from CRS
Study Drug	Placebo 8:00 a.m., Lorcaserin 10mg p.m. prior to departure or Placebo 8:00 a.m., Placebo p.m. prior to	Placebo 8:00 a.m., Lorcaserin 10mg p.m. prior to departure or Placebo 8:00	Placebo 8:00 a.m., Lorcaserin 10mg p.m. prior to departure or Placebo	Placebo 8:00 a.m., Lorcaserin 10mg p.m. prior to departure, or Placebo 8:00 a.m., placebo p.m. prior to departure	Placebo 8:00 a.m.

	departure	a.m., placebo p.m. prior to departure	8:00 a.m., placebo p.m. prior to departure		
--	-----------	--	---	--	--

Study Day	Day 8	Day 9	Day 10	Day 11	Day 12
Study Visit	Eight	Nine	Ten	Eleven	Twelve
Procedure Morning Session	Arrive at IDAS ECG	Arrive at IDAS ECG	Arrive at CRS ECG 10mg Cocaine for PK, Lorcaserin blood levels	Arrive at CRS ECG Cocaine Self Administration	Arrive at IDAS ECG Impulsivity Testing
Procedure Afternoon Session			Three Doses of Cocaine (NexFin monitoring) Cardiovascular & Subjective Ratings Cardiac Biomarkers (4-6 hrs from last dose) Impulsivity Testing Depart from CRS	Cocaine Self Administration Depart from CRS	Physical exam
Study Drug	Lorcaserin 10mg 8:00 a.m., Lorcaserin 10mg p.m. prior to departure. or Placebo 8:00 a.m., placebo p.m. prior to departure	Lorcaserin 10mg 8:00 a.m., Lorcaserin 10mg p.m. prior to departure or Placebo 8:00 a.m., placebo p.m. prior to departure	Lorcaserin 10mg 8:00 a.m., Lorcaserin 10mg p.m. prior to departure or Placebo 8:00 a.m., placebo p.m. prior to departure	Lorcaserin 10mg 8:00 a.m. or Placebo 8:00 a.m.,	

Self-Administration Session (Days 3, 7, and 11)

On days 3, 7, and 11, subjects participate in two self-administrative sessions and will make six choices for cocaine or \$5. The first session will begin at 10 am and the second at 1 pm (see Table 3 below), with each session being 2.5 hours long.

Table 3. Schedule of Cocaine Self Administration Procedure

Time	Choices	8 patients	8 patients
10:00 am	Baseline: VAS, BP/HR, EKG		
10:20 am	Choice 1	0 mg cocaine IV or \$ 5	25 mg cocaine IV or \$ 5
10:35 am	Choice 2	0 mg cocaine IV or \$ 5	25 mg cocaine IV or \$ 5

10:50 am	Choice 3	0 mg cocaine IV or \$ 5	25 mg cocaine IV or \$ 5
11:05 am	Choice 4	0 mg cocaine IV or \$ 5	25 mg cocaine IV or \$ 5

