11:20 am	Choice 5	0 mg cocaine IV or \$ 5	25 mg cocaine IV or \$ 5
11:35 am	Choice 6	0 mg cocaine IV or \$ 5	25 mg cocaine IV or \$ 5
1:00 pm	Baseline: VAS, BP/HR, EKG		
1:20 pm	Choice 1	25 mg cocaine IV or \$ 5	0 mg cocaine IV or \$ 5
1:35 pm	Choice 2	25 mg cocaine IV or \$ 5	0 mg cocaine IV or \$ 5
1:50 pm	Choice 3	25 mg cocaine IV or \$ 5	0 mg cocaine IV or \$ 5
2:05 pm	Choice 4	25 mg cocaine IV or \$ 5	0 mg cocaine IV or \$ 5
2:20 pm	Choice 5	25 mg cocaine IV or \$ 5	0 mg cocaine IV or \$ 5
2:35 pm	Choice 6	25 mg cocaine IV or \$ 5	0 mg cocaine IV or \$ 5

In one session subjects will make six choices between 0 mg i.v. cocaine or money. During the other self-administration session, subjects will make six choices between 25 mg i.v. cocaine or money. The dose of cocaine was chosen based on previous studies showing a significant medication effect on cocaine self-administration (Hart *et al*, 2008). Sessions begin with a baseline period in which participants complete computerized subjective-effects questionnaires, and vital signs are monitored.

The session begins with one “sample” choice, where participant respond on a keyboard under a fixed ratio schedule (FR200; participants are required to press the spacebar 200 times to receive the option). The subsequent five trials are spaced 15-min apart, in which participants had the opportunity to self-administer the same dose of cocaine as the sample dose, or to receive money. A modified progressive ratio of responding is used, in which the first response requirement is a FR200. Following each choice, the response requirement for the chosen option increases by 400, while the response requirement for the non-chosen option does not change. Thus, if a participant only chose cocaine or only chose money, the response requirements would escalate progressively through 600, 1,000, 1,400, 1,800, and 2,200 bar presses (Haney *et al*, 2011).

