The subject would make a series of choices using the PR schedule between ascending value money options (\$5) or cocaine (0 mg or 25 mg/i.v. infusion) using a patient controlled (PCA pump). Choices for money will be verbally indicated to the investigator. Infusions will be made over a 2 min period followed by a 13 min time-out period. Subjects will receive the cash or cocaine doses (0 or 25 mg) immediately after they meet the progressive ratio criteria for each choice, providing vital signs remain within the preset intervals. If the subject chooses all cocaine options in the cocaine choice session and no money, they will receive a maximum of 120 mg cocaine, i.v. Money choices will be given directly to the patient after choice session, but this can only be spent after departing from the CRS. All infusions on this day will be double-blinded and counterbalanced in their presentation among subjects.

Cardiovascular Monitoring During Cocaine Infusions and Cocaine Self-Administration Procedure

Cardiovascular monitoring by continuous measuring heart rate/ECG and blood pressure starting 15 minutes prior to each of the 4 cocaine infusions and continued for at least 60 minutes following each dose. PI/Co-I or their medically qualified designees will be present during all cocaine infusions to monitor and intervene if necessary. For the sessions of cocaine infusions on Day 1, 2, 6, and 10, non-invasive monitoring of cardiac hemodynamics will be performed with the NexFin finger cuff system (Edwards Life Sciences).

Criteria for withholding Cocaine Administration

Cocaine administration will not be initiated if:

- Clinically significant arrhythmias
- Resting pulse > 130 bpm
- QTc increase of greater than 30ms over baseline
- Blood pressure above 165mm Hg systolic and 100mm Hg diastolic.
- Behavioral manifestations of cocaine toxicity (agitation, psychosis, inability to cooperate with study procedures).

If cardiovascular measures have not returned to acceptable levels (heart rate <130 bpm, diastolic pressure <100mmHg, and systolic pressure <165 mmHg, QTc <30ms over baseline), the next session will be delayed by 15 min, after which these measures will be repeated.

Stopping Criteria for Subject Participation

Subject participation will be terminated if any of the following events occur:

The following values do not return to acceptable limits within appropriate time frames (approximately 30 minutes);

- Systolic BP > 180 mm Hg
- Diastolic BP > 120 mm Hg

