Children as defined by NIH (age 18-21 years) will be included in this research. The incidence of severe cocaine abuse/dependence is relatively small in the population of youth less than 18 years old. From a safety perspective, risks of exposure to the proposed study medication and cocaine administration in substance-dependent children under 18 have not been established.

Analysis of Primary Endpoint

1. Safety: Heart rate (HR) and blood pressure (BP) measures during saline infusions will be compared to HR and BP after each cocaine infusion (20 mg and 40 mg doses). Changes in HR and BP induced by cocaine infusion along with lorcaserin will be compared to those without lorcaserin, by cocaine dose level (20 mg and 40 mg doses), using repeated measures analysis of variance (ANOVA). Changes in ECG readings during saline infusion as compared to those taken during cocaine infusions will be reported as summary statistics. Adverse event data will be compiled for lorcaserin and placebo cohorts and presented as summary statistics.
2. Cocaine Self-administration: Repeated measures ANOVA with cocaine dose (0mg, 25mg) and lorcaserin dose (0mg, 10mg, 20mg) as within subject factors will be used to examine differences in mean cocaine choice selection. In addition, a Bayesian analysis will be carried out as described below.
3. Subjective response to cocaine: Subjective response measures (VAS) obtained during saline infusions will be compared between lorcaserin and placebo subjects to those during cocaine infusions by cocaine dose level to determine the extent to which these measures are modified by the administration of lorcaserin using repeated measures ANOVA.
4. Cocaine PK: Plasma concentration-time profiles of cocaine after cocaine infusion during placebo administration (Day 2) will be analyzed to obtain pharmacokinetic parameter estimates of cocaine (Tmax, AUC, apparent t_{1/2}, CL) by individual. These parameters will be compared within subjects on sessions with lorcaserin (Day 6 and 10).

Analysis of Secondary Endpoints

Response inhibition: Commission errors on the IMT will be compared between lorcaserin and placebo subjects to determine the extent to which this measure is modified by the administration of lorcaserin using repeated measures ANOVA.

Safety and tolerability data will be summarized by treatment group.

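### The Day 7 impulsivity test comes after self-administration, so its lorcaserin–placebo difference is a valid total effect but cannot be read as lorcaserin's own effect on response inhibition

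*Combined protocol and SAP*

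**What the plan says.** Appendix 1 schedules the IMT on Days 1, 4, 7 and 10. Analysis of Secondary Endpoints states: "Commission errors on the IMT will be compared between lorcaserin and placebo subjects to determine the extent to which this measure is modified", by repeated measures ANOVA. It does not say which days enter, whether the contrast is a main effect or by day, or how cocaine received on the test day is handled.

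For Day 7:

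- Dosage/Dosage Regimen: "Following Cocaine Self-administration sessions and impulsivity testing the subjects will leave the unit".
- Evaluations by Visit, Study Day 7: the list runs through self-administration session 3, then "Self -Administered cocaine session 4 in afternoon", then the mood and global-impression scales, then "Administer IMT task", then departure.
- Table 2, Day 7 afternoon: "Cocaine Self Administration Impulsivity Testing Depart from CRS".

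On what the subject receives, the Self-Administration Session section describes one session with 0 mg and says "During the other self-administration session, subjects will make six choices between 25 mg i.v. cocaine or money". It adds that a subject who always chooses cocaine is limited: "they will receive a maximum of 120 mg cocaine, i.v". On order, it says: "All infusions on this day will be double-blinded and counterbalanced in their presentation among subjects".

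**The concern.** Primary objective 2 is the effect of lorcaserin on cocaine self-administration. The only secondary objective in the synopsis is its effect on response inhibition. On Day 7 the second is measured after the first has played out. If lorcaserin lowers cocaine choice, treated subjects reach the IMT having received less cocaine than placebo subjects. A difference in commission errors could then reflect the lower intake, a direct effect of lorcaserin, or both. The two could also offset each other and hide a direct effect.

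Day 7 is hard to set aside. It is the only IMT taken after several days on the once-daily step, because the Day 4 test follows a single evening dose.

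**Working it through.** **1. Order of events.** The Dosage/Dosage Regimen sentence says only that departure follows both activities. The visit list and Table 2 each put the test after the second session. The order rests on those two places.

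**2. What precedes each IMT** (Dosage/Dosage Regimen, Evaluations by Visit, Table 2):

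| IMT day | Cocaine scheduled earlier that day | Set by | Group B lorcaserin doses so far |
|---|---|---|---|
| 1 | Ascending infusions | Protocol | None |
| 4 | None scheduled | – | One (evening of Day 3) |
| 7 | Two self-administration sessions | Subject's choices | Four (evenings of Days 3–6) |
| 10 | PK dose and ascending infusions | Protocol, subject to the withholding criteria | The four above, plus five at the twice-daily step |

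The Day 3 self-administration sessions come before the first lorcaserin dose, so treatment cannot have changed them.

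**3. Range of exposure on Day 7.** The plan's own maximum is 120 mg.

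- Six choices (Table 3): 6 × 25 = 150 mg.
- Five choices, leaving out the sample trial described in the text: 5 × 25 = 125 mg.

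Neither gives 120 mg. The passages must be reconciled.

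**4. Possible gap between arms.** Gap = placebo choices × 25 mg × proportional reduction. The reductions of 25% and 50% are columns of the power table, taken here as changes in cocaine choice. The placebo choice counts are assumed.

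| Placebo choices (assumed) | Placebo intake | 25% reduction | 50% reduction |
|---|---|---|---|
| 3 of 6 | 75 mg | 18.75 mg | 37.5 mg |
| 4 of 6 | 100 mg | 25 mg | 50 mg |
| 5 of 6 | 125 mg | 31.25 mg | 62.5 mg |
| 6 of 6 | 150 mg | 37.5 mg | 75 mg |

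If the sample infusion is delivered to everyone rather than chosen, the 4-of-6 row has 3 × 25 = 75 mg open to choice, and the gap is 18.75 to 37.5 mg.

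**5. Time since cocaine.** Table 3 puts the last 25 mg choice at 11:35 am or 2:35 pm, depending on session order. The afternoon session starts at 1:00 pm and lasts 2.5 hours, so it ends at 3:30 pm. A test given right then (the documents state no start time) would come 3 h 55 min or 55 min after the last possible 25 mg choice. Session order alone makes a 3-hour difference between subjects.

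**6. Illustration of the consequence.** Suppose lorcaserin has no direct effect and commission errors move by an assumed 0.2 to 1.0 SD per 100 mg. Shift d = (gap / 100) × slope. With 6 and 12 subjects, √(1/6 + 1/12) = 0.5, so the noncentrality is 2d on 16 degrees of freedom. Two-sided 5% test on Day 7 alone:

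| Gap | Shift | Chance of a significant result |
|---|---|---|
| 25 mg | 0.05–0.25 SD | 5.1%–7.6% |
| 50 mg | 0.10–0.50 SD | 5.4%–15.6% |
| 75 mg | 0.15–0.75 SD | 5.9%–29.2% |

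The slope is not in the documents and its sign is not known. The table shows only how the answer depends on it. The documents contain no power statement for the IMT.

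**The case against.** The strongest reply is that Day 7 is a randomised comparison. A reader might infer from the schedule that it is biased or invalid. It is not: it estimates the total effect of assignment to lorcaserin, including any part that acts through lower cocaine intake, and neither statement of the secondary objective explicitly asks for an effect with cocaine held constant. This stands. The problem is one of interpretation. What remains is that a total effect cannot separate response inhibition from intake, and intake is already a primary outcome.

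A reader might also infer that the repeated measures ANOVA averages over all IMT days. The text does not say so. Such a model can give day-specific contrasts, and the protocol leaves detail to an SAP still to be written. Only the silence can be criticised.

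The milligram gaps rest on assumed choice counts, and subjects whose 25 mg session was in the morning are at least three hours past their last possible active choice when the afternoon choices end. Both points stand, and they are why no size is claimed.

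Finally, Day 4 might be taken as a cocaine-free comparator. It has no scheduled cocaine, but subjects leave the unit each day, Day 4 is an outpatient visit, and a cocaine-positive urine screen is permitted. Use off the unit after the first evening dose is possible.

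**Conclusion.** The point holds as one of interpretation, confined to one of three post-baseline tests of a secondary endpoint. No primary outcome is affected. Two parts of the schedule agree that the Day 7 IMT follows choice-dependent cocaine, and no section says how this is handled.

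The existence of the pathway follows from the documents. Its size does not: the 19 to 75 mg range depends on assumed placebo choices and on the power table's reductions applying to choice, and nothing links milligrams of cocaine to commission errors. Direction is equally open.

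Two stronger responses are not supported. Dropping Day 7 would lose the only IMT after several days at the once-daily step. Adding milligrams received as a covariate would not repair the contrast, because intake is a consequence of treatment.

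**What to change.** Give the Day 7 IMT before the first self-administration session at 10:00 am, and change the Day 7 entries in Dosage/Dosage Regimen, Evaluations by Visit and Table 2 to match. This removes same-day chosen cocaine from the test in both arms and keeps the measurement. The number of lorcaserin doses before the test is unchanged, since every subject takes placebo on the morning of Day 7. The cost is moving one task. The small downside is that Day 7 becomes a test without same-day cocaine, unlike Days 1 and 10, so the SAP should contrast lorcaserin with placebo separately by day.

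If the visit order cannot change, the SAP should:

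- report IMT contrasts by day;
- make Day 10, adjusted for Day 1, the main contrast, since both follow protocol-set cocaine;
- describe Day 4 as having no scheduled cocaine;
- label Day 7 a total effect and show it beside the milligrams received, without adjusting for them.

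That alternative costs SAP wording only. Under either option, reconcile the stated 120 mg maximum with the six 25 mg choices in Table 3, and Table 3's 8 + 8 = 16 patients with the planned 18.

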Record brief substance craving scale, timeline follow back cocaine use, and drug use history.
Verify inclusion and exclusion.
Schedule subject for Day 1 visit as soon as possible.

Study Day 1

Arrive at CRS unit.
Collect urine for pregnancy test and urine drug screen.
Perform and record Breathalyzer.
Administer COWS if opioid user.
Perform and record vital signs.
Perform a 12-Lead ECG.
Perform a brief physical exam and continuous cardiovascular monitoring.
Administer placebo in morning.
Administer cocaine for Dosing session 1.
Record brief substance craving scale.
Update concomitant medications.
Record Visual Analog Scale (VAS).
Record adverse events.
Conduct clinical assessments (POMS, CGI-I, C-SSRS).
Administer Immediate Memory Task (IMT).
Leave CRS unit.

Study Day 2

Arrive on CRS unit.
Collect urine for pregnancy test and urine drug screen.
Perform and record Breathalyzer and vital signs.
Administer COWS if opioid user.
Perform a 12-Lead ECG.
Perform a brief physical exam and continuous cardiovascular monitoring.

Administer placebo in morning.
Administer cocaine for PK.
Record brief substance craving scale.
Update concomitant medications.
Record VAS and adverse events.
Administer cocaine for Dosing session 2.
Conduct clinical assessments (POMS, CGI-I).
Leave CRS unit.

Study Day 3

Arrive on CRS unit.
Collect urine for pregnancy test and urine drug screen.
Perform and record Breathalyzer and vital signs.
Administer COWS if opioid user.
Perform a 12-Lead ECG, brief physical exam, and continuous cardiovascular monitoring.
Administer placebo in morning
Self-Administered cocaine session 1 in morning.
Self-Administered cocaine session 2 in afternoon.
Record brief substance craving scale.
Update concomitant medications.
Record VAS and AE.
Conduct clinical assessments (POMS, CGI-I).
Administer placebo/lorcaserin in evening
Leave CRS unit.

Study Day 4

Arrive at IDAS
Administer placebo in morning
Collect urine for pregnancy test and urine drug screen
Perform and record Breathalyzer and vital signs.
Perform a 12-Lead ECG.
Record brief substance craving scale and AE.
Administer COWS if opioid user.
Update concomitant medications.
Conduct clinical assessments (POMS, CGI-I).
Administer IMT task
Administer placebo/lorcaserin in evening
Leave IDAS.

Study Day 5

Arrive at IDAS

Administer placebo in morning
Collect urine for pregnancy test and urine drug screen.
Perform and record Breathalyzer and vital signs.
Perform a 12-Lead ECG.
Record brief substance craving scale and AE.
Administer COWS if opioid user.
Update concomitant medications.
Conduct clinical assessments (POMS, CGI-I, and C-SSRS).
Administer placebo/lorcaserin in evening
Leave IDAS.

Study Day 6

Arrive on CRS unit
Administer placebo in morning
Collect urine for pregnancy test and urine drug screen.
Perform and record Breathalyzer and vital signs.
Perform a 12-Lead ECG and continuous cardiovascular monitoring.
Record brief substance craving scale, VAS, and AE.
Administer COWS if opioid user.
Update concomitant medications.
Administer cocaine for PK.
Measure lorcaserin PK
Administer cocaine for Dosing session 3.
Conduct clinical assessments (POMS, CGI-I).
Administer placebo/lorcaserin in evening
Leave CRS unit.

Study Day 7

Arrive on CRS unit
Administer placebo in morning
Collect urine for pregnancy test and urine drug screen.
Perform and record Breathalyzer and vital signs.
Perform a 12-Lead ECG and brief physical exam.
Record brief substance craving scale, VAS and AE.
Administer COWS if opioid user.
Update concomitant medication.
Self -Administered cocaine session 3 in morning.
Self -Administered cocaine session 4 in afternoon.
Conduct clinical assessments (POMS, CGI-I).
Administer IMT task.
Leave CRS unit

Study Day 8

Arrive at IDAS

Administer placebo/lorcaserin in morning

Collect urine for pregnancy test and urine drug screen.

Perform and record Breathalyzer and vital signs.

Administer COWS if opioid user.

Perform a 12-Lead ECG and brief physical exam.

Record brief substance craving scale, VAS and AE.

Update concomitant medications.

Conduct clinical assessments (POMS, CGI-I, and C-SSRS).

Administer placebo/lorcaserin in evening.

Leave IDAS.

Study Day 9

Arrive at IDAS

Administer placebo/lorcaserin in morning

Collect urine for pregnancy test and urine drug screen.

Perform and record Breathalyzer and vital signs.

Perform a 12-Lead ECG.

Record brief substance craving scale and AE.

Administer COWS if opioid user.

Update concomitant medications.

Conduct clinical assessments (POMS, CGI-I, and C-SSRS).

Administer placebo/lorcaserin in evening.

Leave IDAS.

Study Day 10

Arrive on CRS unit

Administer placebo/lorcaserin in morning

Collect urine for pregnancy test and urine drug screen.

Perform and record Breathalyzer and vital signs.

Perform a 12-Lead ECG and continuous cardiovascular monitoring.

Record brief substance craving scale, VAS, and AE.

Administer COWS if opioid user.

Update concomitant medications.

Administer cocaine for PK.

Measure lorcaserin PK.

Conduct clinical assessments (POMS, CGI-I).

Administer cocaine for Dosing session 4.

Administer IMT task

Administer placebo/lorcaserin in evening
Leave CRS unit.

Study Day 11

Arrive on CRS unit
Administer placebo/lorcaserin in morning
Collect urine for pregnancy test and urine drug screen.
Collect blood for clinical laboratory tests (serum chemistry and hematology).
Perform and record Breathalyzer and vital signs.
Perform a 12-Lead ECG and continuous cardiovascular monitoring.
Record brief substance craving scale, VAS and AE.
Administer COWS if opioid user.
Update concomitant medication.
Self -Administered cocaine session 5 in morning.
Self -Administered cocaine session 6 in afternoon.
Conduct clinical assessments (POMS, CGI-I).
Leave CRS unit.

Study Day 12

Arrive at IDAS
Collect urine for pregnancy test and urine drug screen.
Perform and record Breathalyzer and vital signs.
Perform a 12-Lead ECG.
Record brief substance craving scale and AE.
Administer COWS if opioid user.
Update concomitant medication.
Conduct clinical assessments (POMS, CGI-I, Stroop, and XY Go-No Go).
PI (or designee) conduct assessment for lorcaserin side effects.
Leave IDAS

Follow-Up Days (Day 15, 19) Conducted at IDAS

Collect urine for pregnancy test and urine drug screen.
Perform and record Breathalyzer and vital signs.
Perform a 12-Lead ECG and brief physical exam (Day 19 only).
Record brief substance craving scale and timeline follow back cocaine use.
Update concomitant medication.
Conduct clinical assessments (POMS, CGI-I, and C-SSRS).

Table 2. Overview of Study Procedures

Study Day	Day 1	Day 2
Study Visit	One	Two
Procedure Morning Session	Arrive at CRS, Three Screening Doses of Cocaine (NexFin monitoring)	Arrive at CRS 10mg Cocaine for PK
Procedure Afternoon Session	Impulsivity Testing Depart from CRS	Three Doses of Cocaine, Cardiovascular (NexFin monitoring) Cardiac Biomarkers (4-6 hrs from last dose) Subjective Ratings Depart from CRS
Study Drug	Placebo 8:00 a.m.	Placebo 8:00 a.m

Study Day	Day 3	Day 4	Day 5	Day 6	Day 7
Study Visit	Three	Four	Five	Six	Seven Arrive at CRS ECG
Procedure Morning Session	Arrive at CRS Cocaine Self Administration	Arrive at IDAS ECG Impulsivity Testing	Arrive at IDAS ECG	Arrive at CRS ECG 10mg Cocaine for PK, Lorcaserin blood levels	Cocaine Self Administration
Procedure Afternoon Session	Cocaine Self Administration Depart from CRS			Three Doses of Cocaine (NexFin monitoring) Cardiovascular & Subjective Ratings Cardiac Biomarkers (4-6 hrs from last dose) Depart from CRS	Cocaine Self Administration Impulsivity Testing Depart from CRS
Study Drug	Placebo 8:00 a.m., Lorcaserin 10mg p.m. prior to departure or Placebo 8:00 a.m., Placebo p.m. prior to	Placebo 8:00 a.m., Lorcaserin 10mg p.m. prior to departure or Placebo 8:00	Placebo 8:00 a.m., Lorcaserin 10mg p.m. prior to departure or Placebo	Placebo 8:00 a.m., Lorcaserin 10mg p.m. prior to departure, or Placebo 8:00 a.m., placebo p.m. prior to departure	Placebo 8:00 a.m.

	departure	a.m., placebo p.m. prior to departure	8:00 a.m., placebo p.m. prior to departure		
--	-----------	--	---	--	--

Study Day	Day 8	Day 9	Day 10	Day 11	Day 12
Study Visit	Eight	Nine	Ten	Eleven	Twelve
Procedure Morning Session	Arrive at IDAS ECG	Arrive at IDAS ECG	Arrive at CRS ECG 10mg Cocaine for PK, Lorcaserin blood levels	Arrive at CRS ECG Cocaine Self Administration	Arrive at IDAS ECG Impulsivity Testing
Procedure Afternoon Session			Three Doses of Cocaine (NexFin monitoring) Cardiovascular & Subjective Ratings Cardiac Biomarkers (4-6 hrs from last dose) Impulsivity Testing Depart from CRS	Cocaine Self Administration Depart from CRS	Physical exam
Study Drug	Lorcaserin 10mg 8:00 a.m., Lorcaserin 10mg p.m. prior to departure. or Placebo 8:00 a.m., placebo p.m. prior to departure	Lorcaserin 10mg 8:00 a.m., Lorcaserin 10mg p.m. prior to departure or Placebo 8:00 a.m., placebo p.m. prior to departure	Lorcaserin 10mg 8:00 a.m., Lorcaserin 10mg p.m. prior to departure or Placebo 8:00 a.m., placebo p.m. prior to departure	Lorcaserin 10mg 8:00 a.m. or Placebo 8:00 a.m.,	

Self-Administration Session (Days 3, 7, and 11)

On days 3, 7, and 11, subjects participate in two self-administrative sessions and will make six choices for cocaine or \$5. The first session will begin at 10 am and the second at 1 pm (see Table 3 below), with each session being 2.5 hours long.

Table 3. Schedule of Cocaine Self Administration Procedure

Time	Choices	8 patients	8 patients
10:00 am	Baseline: VAS, BP/HR, EKG		
10:20 am	Choice 1	0 mg cocaine IV or \$ 5	25 mg cocaine IV or \$ 5
10:35 am	Choice 2	0 mg cocaine IV or \$ 5	25 mg cocaine IV or \$ 5

10:50 am	Choice 3	0 mg cocaine IV or \$ 5	25 mg cocaine IV or \$ 5
11:05 am	Choice 4	0 mg cocaine IV or \$ 5	25 mg cocaine IV or \$ 5
11:20 am	Choice 5	0 mg cocaine IV or \$ 5	25 mg cocaine IV or \$ 5
11:35 am	Choice 6	0 mg cocaine IV or \$ 5	25 mg cocaine IV or \$ 5
1:00 pm	Baseline: VAS, BP/HR, EKG		
1:20 pm	Choice 1	25 mg cocaine IV or \$ 5	0 mg cocaine IV or \$ 5
1:35 pm	Choice 2	25 mg cocaine IV or \$ 5	0 mg cocaine IV or \$ 5
1:50 pm	Choice 3	25 mg cocaine IV or \$ 5	0 mg cocaine IV or \$ 5
2:05 pm	Choice 4	25 mg cocaine IV or \$ 5	0 mg cocaine IV or \$ 5
2:20 pm	Choice 5	25 mg cocaine IV or \$ 5	0 mg cocaine IV or \$ 5
2:35 pm	Choice 6	25 mg cocaine IV or \$ 5	0 mg cocaine IV or \$ 5

In one session subjects will make six choices between 0 mg i.v. cocaine or money. During the other self-administration session, subjects will make six choices between 25 mg i.v. cocaine or money. The dose of cocaine was chosen based on previous studies showing a significant medication effect on cocaine self-administration (Hart *et al*, 2008). Sessions begin with a baseline period in which participants complete computerized subjective-effects questionnaires, and vital signs are monitored.

The session begins with one “sample” choice, where participant respond on a keyboard under a fixed ratio schedule (FR200; participants are required to press the spacebar 200 times to receive the option). The subsequent five trials are spaced 15-min apart, in which participants had the opportunity to self-administer the same dose of cocaine as the sample dose, or to receive money. A modified progressive ratio of responding is used, in which the first response requirement is a FR200. Following each choice, the response requirement for the chosen option increases by 400, while the response requirement for the non-chosen option does not change. Thus, if a participant only chose cocaine or only chose money, the response requirements would escalate progressively through 600, 1,000, 1,400, 1,800, and 2,200 bar presses (Haney *et al*, 2011).

The subject would make a series of choices using the PR schedule between ascending value money options (\$5) or cocaine (0 mg or 25 mg/i.v. infusion) using a patient controlled (PCA pump). Choices for money will be verbally indicated to the investigator. Infusions will be made over a 2 min period followed by a 13 min time-out period. Subjects will receive the cash or cocaine doses (0 or 25 mg) immediately after they meet the progressive ratio criteria for each choice, providing vital signs remain within the preset intervals. If the subject chooses all cocaine options in the cocaine choice session and no money, they will receive a maximum of 120 mg cocaine, i.v. Money choices will be given directly to the patient after choice session, but this can only be spent after departing from the CRS. All infusions on this day will be double-blinded and counterbalanced in their presentation among subjects.

Cardiovascular Monitoring During Cocaine Infusions and Cocaine Self-Administration Procedure

Cardiovascular monitoring by continuous measuring heart rate/ECG and blood pressure starting 15 minutes prior to each of the 4 cocaine infusions and continued for at least 60 minutes following each dose. PI/Co-I or their medically qualified designees will be present during all cocaine infusions to monitor and intervene if necessary. For the sessions of cocaine infusions on Day 1, 2, 6, and 10, non-invasive monitoring of cardiac hemodynamics will be performed with the NexFin finger cuff system (Edwards Life Sciences).

Criteria for withholding Cocaine Administration

Cocaine administration will not be initiated if:

- Clinically significant arrhythmias
- Resting pulse > 130 bpm
- QTc increase of greater than 30ms over baseline
- Blood pressure above 165mm Hg systolic and 100mm Hg diastolic.
- Behavioral manifestations of cocaine toxicity (agitation, psychosis, inability to cooperate with study procedures).

If cardiovascular measures have not returned to acceptable levels (heart rate <130 bpm, diastolic pressure <100mmHg, and systolic pressure <165 mmHg, QTc <30ms over baseline), the next session will be delayed by 15 min, after which these measures will be repeated.

Stopping Criteria for Subject Participation

Subject participation will be terminated if any of the following events occur:

The following values do not return to acceptable limits within appropriate time frames (approximately 30 minutes);

- Systolic BP > 180 mm Hg
- Diastolic BP > 120 mm Hg
- Heart rate > (220 – age x 0.85) bpm
- QTc > 470ms
- Participants must continue to meet other inclusion criteria in order to remain in the protocol

ADVERSE EXPERIENCE REPORTING AND DOCUMENTATION

Adverse Events

Adverse Events (AEs) will be identified through daily interviews with participants and noted at any visit. The data will be entered on the standard VCU IRB AE and SAE forms. Continuous logs of all SAEs and AEs will be maintained. SAEs will be reported to the VCU IRB, the NIDA PO, the DSMB and the US FDA (when appropriate) as described above. In addition to immediate reports where appropriate, there will be annual reports and descriptions in the results section of publications.

Table 4. AE Severity Grading

Severity (Toxicity Grade)	Description
Mild (1)	Transient or mild discomfort; no limitation in activity; no medical intervention or therapy required. The subject may be aware of the sign or symptom but tolerates it reasonably well.
Moderate (2)	Mild to moderate limitation in activity, no or minimal medical intervention/therapy required.
Severe (3)	Marked limitation in activity, medical intervention/therapy required, hospitalizations possible.
Life-threatening (4)	The subject is at risk of death due to the adverse experience as it occurred. This does not refer to an experience that hypothetically might have caused death if it were more severe.

AE Relationship to Study Drug

The relationship of an AE to the study drug will be assessed using the following the guidelines in 5. Table 5. AE Relationship to Study Drug

Relationship to Drug	Comment
Definitely	Previously known toxicity of agent; or an event that follows a reasonable temporal sequence from administration of the drug; that follows a known or expected response pattern to the suspected drug; that is confirmed by stopping or reducing the dosage of the drug; and that is not explained by any other reasonable hypothesis.
Probably	An event that follows a reasonable temporal sequence from administration of the drug; that follows a known or expected response pattern to the suspected drug; that is confirmed by stopping or reducing the dosage of the drug; and that is unlikely to be explained by the known characteristics of the subject's clinical state or by other interventions.
